#### 9.4.1 Ovaprene™ Safety Cycle - Visits and procedures:

#### a) Visit OS1, the day following the end of menses (approximately cycle day 6):

- Diary review, AEs, medications, and indications for a directed physical exam, wet mount, and other tests will be managed as described for Visit 2 (BP1).
- Blood will be drawn for CBC, serum chemistries, and serum ferritin.
- The participant will undergo a pelvic exam:
  - o Signs of irritation of the external genitalia, cervix, and vagina, as observed with the naked eye, will be noted.
  - o A colposcopic exam will be completed.

Version: 06.00 (FINAL) Date: June 13, 2019

- o Cervical mucus will be collected for pH.
- o Vaginal sample(s) will be collected for ferrous gluconateo, pH, Nugent score, and microflora.
- o At sites other than EVMS, vaginal samples will be collected for antibacterial activity and soluble markers.
- The participant will insert Ovaprene™ using written instructions, with assistance if needed. The clinician will check the placement.
- At the EVMS site only:
  - o 0.5, 1, 2, 4, and 6 hours after insertion: p
    - Vaginal sample(s) will be collected for ferrous gluconate and pH
  - o At 6 hours after insertion, if possible:
    - Vaginal sample(s) for antibacterial activity and soluble markers will be collected.
- The participant will be instructed to abstain from intercourse and other vaginal activities until after Visit OS5

#### b) Visit OS2, 24 hours after insertion:

- Diary review, AEs, medications, and indications for a directed physical exam, wet mount, and other tests will be managed as described for Visit 2 (BP1).
- The participant will undergo a pelvic exam:
  - o Signs of irritation of the external genitalia, cervix, and vagina, as observed with the naked eye, will be noted.
  - o The position of the device relative to the cervix will be noted.
  - o Vaginal sample(s) will be collected for ferrous gluconate, pH, Nugent score, microflora, antibacterial activity, and soluble markers.
- An ovulation predictor kit (OPK) with instructions will be dispensed. The participant will be instructed to:
  - o Begin daily urine testing on day 10 of that cycle (adjusted as needed to normal cycle length); and
  - o Contact the study coordinator when the OPK test yields a "high" result, if that takes place before OS3 is scheduled. If possible, OS3 will be scheduled for that day or the next day. If that is not possible, OS3 will take place 7-9 days after insertion (approximately cycle day 13 -15).
- c) Visit OS3, 7-9 days after insertion (approximately cycle day 13 -15, unless a "high" OPK result takes place):

° It is expected that ferrous gluconate will not be found in the vaginal sample before the device is inserted. Samples taken before insertion will serve as a negative control.

<sup>p Samples will be collected at as many of these timepoints as possible.

Version: 06.00 (FINAL) Date: June 13, 2019

- The procedures described above for Visit OS2 will be completed, except that no OPK will be dispensed.
- In addition, cervical mucus will be collected for ferrous gluconateq and pH.

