#### 5.2 OBJECTIVES

- 1. Primary: Changes in PCT results due to device use
  - a) Demonstrate successful barrier performance, as defined in **Appendix 3** during Ovaprene™ use in women who were able to demonstrate good results in a baseline cycle. An average of fewer than 5 progressively motile sperm in the cervical mucus per high powered field (HPF) is considered indicative of acceptable barrier function.
- 2. Secondary: Release of active component from device
  - a) Determine the levels of ferrous gluconate in CVF before sex that are associated with fewer than 5 progressively motile sperm per high powered field (HPF) in the cervical mucus (i.e. success) after sex, during ovulation.
  - b) Determine how long after insertion it takes to reach these levels
  - c) Determine whether these levels are still present 27-29 days after device insertion
  - d) Determine the levels of ferrous gluconate in CVF after sex at ovulation with the device in place and if different from before sex, how much time is needed to return to pre-sex levels.
  - e) Demonstrate the device's effect on CVF pH.
  - f) Assess residual amount of ferrous gluconate in Ovaprene™ devices that have been worn over a cycle of use.
- 3. Secondary: Safety
  - a) Assess systemic and genital safety using traditional endpoints and Ovaprene-specific endpoints
- 4. Tertiary: Acceptability
  - a) Assess acceptability of Ovaprene™ when left in place as directed for 3 cycles.
- 5. Tertiary: Fit
  - a) Assess fit of Ovaprene™.
  - b) Assess ability of women to insert, position, and remove the device
  - c) Assess the position of Ovaprene™ before and after intercourse and the relationship of position to other endpoints

Version: 06.00 (FINAL) Date: June 13, 2019

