#### 8.1 INCLUSION CRITERIA

- 1. Women aged 18-50 years, inclusive
- 2. General good health, by volunteer history and per investigator judgment
- 3. History of regular menstrual cycles of 24-35 days (inclusive), by volunteer report
- 4. History of Pap tests and follow-up consistent with standard medical practice or willing to undergo a Pap test at Visit 1.
- 5. Protected from pregnancy by female tubal sterilization
- 6. Willing to abstain from or engage in intercourse with and without condoms and to abstain from other vaginal activitya as required in the protocol
- 7. In a mutually monogamous relationship for at least the last four months with a male partner who:
  - a. Is at least 18 years old;
  - b. Has no known risk for STIs;
  - c. Is willing and able to comply with protocol requirements including sexual activity/ abstinence and condom use requirements; and
  - d. Can engage in vaginal intercourse with the participant, with and without condoms, as specified in protocol
- 8. Vaginal and cervical anatomy that, in the opinion of the investigator, lends itself to easy colposcopy and genital tract sample collection
- 9. Willing to give voluntary consent, sign an informed consent form and comply with study procedures as required by the protocol

<sup>a "Other vaginal activity" includes insertion of vaginal medications/products other than the study product (prescription or over-the-counter), as well as insertion of sex toys, fingers, or anything else into the vagina. Tampons may be used during all days of menses in the Baseline PCT and Caya PCT cycles, but only during the first three days of menses in Ovaprene cycles.

Version: 06.00 (FINAL) Date: June 13, 2019

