# e) Visit OS5, 21-23 days after insertion (approximately cycle day 27-29, or sooner if menses is expected to begin):

- An acceptability questionnaire will be administered.
- Blood will be drawn for CBC, serum chemistries, and serum ferritin.
- The procedures described above for Visit OS2 will be completed, except that no OPK will be dispensed.
- Ovaprene™ will be removed and stored for later analysis.
- A colposcopic exam will be completed.
- Cervical mucus will be collected for ferrous gluconate and pH.
- The participant will next undergo an Ovaprene™ PCT cycle. She will be instructed to:
  - o Call at the onset of her next menses to tentatively schedule Visit OP1 on the day following the end of menses. Adjustments to this visit will be made as needed.
  - Use non-spermicidal, lubricated condoms (dispense as needed at this visit) from the first day of her next menses until day 10 of that cycle, and to abstain from intercourse and other vaginal activityr starting on Day 10 until after Visit OP2, the CMC visit.

<sup>q Assaying for ferrous gluconate in the cervical mucus is considered exploratory throughout the study.

"Other vaginal activity" includes insertion of vaginal medications/products other than the study product (prescription or over-the-counter), as well as insertion of sex toys, fingers, or anything else into the vagina. Tampons may be used during all days of menses in the Baseline PCT and Caya PCT cycles, but only during the first three days of menses in Ovaprene cycles.

Version: 06.00 (FINAL) Date: June 13, 2019

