Uniform mixing of the spermiostatic components throughout the silicone matrix is controlled during the ring manufacturing process. In an *in vitro* model simulating *in vivo* conditions, ferrous gluconate (FG) is released from the ring immersed in synthetic vaginal fluid in three different stages. These consist of an initial burst (day 1), erosion (days 2-7) and diffusion (days 5-35). Release studies evaluated the cumulative concentration of each component and demonstrated that the average concentration of FG throughout the testing period exceeded the minimal levels required for spermiostatic activity based on literature values.

Ovaprene™ already meets the necessary toxicology requirements for human studies and regulatory approval. Ovaprene™ has been found non-mutagenic and non-clastogenic via Gene Mutation testing, Chromosomal Aberration testing, and Rodent Bone Marrow Micronucleus Assay testing, and has met the International Standards Organization (ISO 10993-10 guidelines) requirements of the Kligman Maximization Test, Rabbit Pyrogen Test, and Intracutaneous Injection Test. A four-week Muscular Implantation test in rabbits demonstrated no difference compared to controls, and a Primary Vaginal Repeat Exposure test in rabbits demonstrated that the extracts of Ovaprene™ are non-irritating.

The Ovaprene™ ring was miniaturized to evaluate contraceptive activity in rabbits. The adapted device was 100% effective in preventing pregnancy in this model.

An open label, single-arm, observational study was conducted with Ovaprene™ in sexually active women.¹ Twenty women were enrolled. Baseline Pap tests, vaginal cultures and colposcopy were performed with follow-up post-coital testing and acceptability questionnaires. Participant questionnaires revealed no pain, bleeding, or discharge and no colposcopic abnormalities were observed. Semi-quantitative cultures yielded no significant changes in vaginal flora. Post-coital testing assessed preliminary contraceptive activity by assessing motile sperm in ten high powered fields. There were no normal, forward-moving sperm seen in the

Version: 06.00 (FINAL) Date: June 13, 2019

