# 14. STATISTICS

# 14.1 SAMPLE SIZE JUSTIFICATION

Approximately 45 participants will be enrolled, with the intent that approximately 25 will complete the study. Statistical considerations were not used to determine the size of the study population; rather, the study size was determined according to the maximum number of subjects that could feasibly be enrolled and complete this rigorous protocol in a reasonable time frame.

Version: 06.00 (FINAL) Date: June 13, 2019

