- c) Levels of ferrous gluconate in CVF before sex that are associated with fewer than 5 progressively motile sperm per HPF in the cervical mucus after sex (i.e. success), during ovulation. Summary statistics of sample size, mean, median, standard deviation, and IQR will be presented by visit.
- d) Levels of ferrous gluconate in CVF at multiple time points in the safety cycle in the absence of coitus. This will allow the estimation of how long after insertion it takes to reach the target concentration levels associated with success and whether target levels are still present up to 29 days after insertion. Summary statistics of sample size, mean, median, standard deviation, and IQR will be presented by visit and assessment timepoint.
- e) Levels of ferrous gluconate in CVF before and at multiple time points after sex at ovulation with the device in place. This will allow determination of whether they are different from before sex and, if so, how much time is needed to return to pre-sex levels at all visits in Ovaprene® PCT cycles in both vaginal and cervical fluid. Summary statistics of sample size, mean, median, standard deviation, and IQR will be presented by visit and assessment time-point.
- f) Vaginal pH (from Vaginal Sample CRF) and cervical pH (from Cervical Mucus CRF) before and after sex in the absence and presence of the device. Six-number summary for the observed values and difference between pre-sex and after sex will be presented by visit. For the study site (EVMS only) with multiple timepoints at a visit, the summary will be done at each timepoint. The average of pH values within each visit over the multiple timepoints will be calculated for each subject, and then be summarized. The goal of these assessments during the Ovaprene® safety cycle is to look at the effect of study device in the absence of sex.
- g) Residual amount of ferrous gluconate in Ovaprene® devices that have been worn over a cycle of use. Six-number summary statistics will be presented by visit and by duration of time the device was worn (1-7 days, 8-14 days, 15-21 days, 22-28 days and >28 days).
- h) Cervical mucus score. Summary statistics mean, median, standard deviation, and IQR will be presented by visit. The number and percent of subjects with cervical mucus score ≥ 10 in each Ovaprene cycle will also be presented. For the summary of cervical mucus score ≥ 10, cervical mucus data will only be used from the cycle that occurs after the highest OPK result for that cycle.

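### Safety-cycle ferrous gluconate in fluid is summarised by visit label although OS3 and OS5 pool different days of wear; it should also be analysed by actual time since insertion

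*Protocol*

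**What the plan says.** Protocol Section 5.2 first asks for the FG level in cervicovaginal fluid before sex that goes with PCT success (2a). It then sets two questions about time since insertion: "Determine how long after insertion it takes to reach these levels" (2b), and whether the levels are still present at 27-29 days after insertion (2c). Section 6 assigns the two time questions to the safety cycle.

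In that cycle (Section 9.4.1), FG is sampled before insertion, at 0.5-6 hours (EVMS only), at 24 hours (OS2), at OS3, at 14-16 days (OS4) and at 21-23 days (OS5). OS3 has a nominal window of 7-9 days, but if the ovulation predictor kit (OPK) reads high before the visit is scheduled, "If possible, OS3 will be scheduled for that day or the next day". OS4 and OS5 may be earlier if menses is expected. The text under OS4 also asks that OS5 be booked from the woman's usual cycle length, late in the cycle but before menses. In the PCT cycles, OP2 follows the OPK high result (Section 9.5.1 b). Eligibility allows a "History of regular menstrual cycles of 24-35 days (inclusive), by volunteer report" (Section 8.1).

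For safety-cycle FG in fluid, SAP 3.6 d) states: "Summary statistics of sample size, mean, median, standard deviation, and IQR will be presented by visit and assessment timepoint". SAP 3.6 c) summarises the success-associated values by visit. Only residual FG in the removed device, in SAP 3.6 g), is also summarised "by duration of time the device was worn", in bins of 1-7, 8-14, 15-21, 22-28 and more than 28 days. The planned FG-in-fluid tables split by site and by PCT success, and the only planned graph (SAP 4.2.3) is of vaginal pH.

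**The concern.** Objectives 2b and 2c are about elapsed time with the device in place. A visit row answers them only if the visit label fixes that time. OS3 follows ovulation when ovulation is early, and OS5 follows menses, so their rows mix women at different days of wear. An OS3 median then cannot be read as a level at 7-9 days, nor an OS5 median as a level at a stated late day.

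The benchmark has a related gap. The levels in 2b and 2c are those of 2a, which come from the pre-sex samples at OP2. They will be set beside safety-cycle rows with no statement of how long the device had been worn when they were taken.

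With about 25 completers planned, a few women with short cycles could shift a visit median.

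**Working it through.** **Inputs from the documents.** Insertion at about cycle day 6 (Protocol 9.4.1 a and 9.5.1 a). Cycle length L of 24-35 days (8.1). OS3 at 7-9 days unless brought forward. OS4 at 14-16 days. OS5 at 21-23 days or sooner. OP2 on the day of the OPK high result or the next. In the 28-day model cycle (Table 11) the high result is on day 13.

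**Assumptions.** Insertion exactly on day 6. OPK high on day L - 15, which reproduces day 13 at L = 28.

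**The protocol's own conversions.** Cycle day = 6 + days of wear. OS3: 6+7 to 6+9 = 13-15. OS4: 6+14 to 6+16 = 20-22. OS5: 6+21 to 6+23 = 27-29. All three match the protocol.

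**Days of wear by cycle length.** OP2 = (L - 15) - 6, or one day later. OS3 takes the same value if that is before day 7, and is otherwise 7-9. OS5 can be no later than L - 6, within its 21-23-day window.

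| L | OPK high (day) | OS3 wear | OP2 wear | OS5 wear |
|---|---|---|---|---|
| 24 | 9 | 3-4 | 3-4 | at most 18 |
| 25 | 10 | 4-5 | 4-5 | at most 19 |
| 26 | 11 | 5-6 | 5-6 | at most 20 |
| 27 | 12 | 6-7 | 6-7 | at most 21 |
| 28 | 13 | 7-9 | 7-8 | 21-22 |
| 30 | 15 | 7-9 | 9-10 | 21-23 |
| 35 | 20 | 7-9 | 14-15 | 21-23 |

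OS3 therefore covers about 3-9 days, OP2 about 3-15 and OS5 about 18-23. If testing in a 24-day cycle starts only on day 10, its OP2 value becomes 4-5 days. If insertion ranges over cycle days 4-8 (assumed), OP2 covers (24 - 15) - 8 = 1 to (35 - 15 + 1) - 4 = 17 days.

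**Visits not affected.** The 0.5-6 hour samples and OS2 are timed from insertion. OS4 at 14-16 days ends on cycle day 22, before menses even when L = 24. With insertion on day 8, 24 - 8 = 16 days are still available.

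**The late question.** 27-29 days after insertion is cycle day 6+27 to 6+29 = 33-35. Only cycles of 33 days or more reach it (L - 6 at least 27), and only outside the 21-23-day OS5 window. Booking OS5 late in the cycle, as the OS4 text asks, would allow up to 35 - 6 = 29 days. Protocol Section 4 words the same question as 24-35 days of use, and SAP 3.6 d) as up to 29 days.

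**The case against.** Much of the sampling is sound. Early attainment is covered: SAP 3.6 a) and b) plan an insertion-anchored release curve and a check against 8.2 µg/mL over the first 4-6 hours at one site, and OS2 adds 24 hours at every site. A reader might infer that every visit mixes days of wear, or that time to reach a level cannot be shown at all. The documents support neither. What is blurred is attainment between 24 hours and day 14, and the late reading.

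OP2 might be taken for a design fault. It is not: objective 2a asks for the level before sex at ovulation, and OPK timing delivers that. Only the missing days of wear are at issue.

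The OS3 shift is confined to short cycles, and the documents give no cycle-length distribution, so the number of women affected is unknown. The OS3 heading is less clear than the text under OS2. If OS3 followed the high result whenever it fell, the spread would be about 3-15 days, but the OS2 text supports only an earlier visit.

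A reader might also infer that short cycles inflate the OS3 and OP2 levels, or put a fold change on the effect. That needs an in vivo rate of decline, which the documents do not give. Protocol 11.1 describes in vitro phases that overlap at days 5-7, and Section 4 says the device is designed to hold release above a minimum for about 35 days.

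Finally, the study is descriptive and all data will be listed by subject and date, so wear time could be worked out afterwards. That is true, but it leaves the answer to two stated objectives outside the planned analysis.

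**Conclusion.** The point holds for OS3 and OS5 in the safety cycle, and as a reporting gap for OP2. Under the two labelled assumptions the OS3 row pools about 3-9 days of wear rather than 7-9, OS5 about 18-23, and the OP2 benchmark about 3-15. Mixing of wear times follows from the visit rules. Its effect on FG values cannot be sized or signed from the documents. SAP 3.6 d) is therefore a weaker way to answer 2b and 2c than the method the SAP already applies to residual FG. The mismatch between 27-29 days in the objective and 21-23 days at OS5 matters more for persistence, because no choice of analysis axis can supply late samples that were not taken.

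**What to change.** - **SAP 3.6 d):** derive time since insertion for each safety-cycle fluid FG sample (sample date and time minus insertion date and time). Plot individual FG against it. Tabulate at about 24 hours and at 2-7, 8-14, 15-21, 22-28 and more than 28 days, in line with g), and show the number of samples at 27-29 days. Read time to reach and persistence from these displays. Keep the by-visit table: the g) boundaries cut through OS4 (14-16 days) and OS5 (21-23 days), so the plot and the visit rows are both needed.
- **SAP 3.6 c):** report days of wear with the OP2 success-associated values.
- **Leave alone:** a) is already on time since insertion, and e) must stay on time relative to sex, or the return-to-pre-sex question (objective 2d) is lost.
- **Reconcile:** the 27-29 days after insertion in objective 2c, the 21-23 days in the OS5 heading, and the late-in-cycle booking instruction under OS4.

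The analysis changes cost SAP wording and programming. Insertion and sampling both take place at clinic visits, so the dates should be in the data (assumed). They change no visit and need no new sample.

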# d) Visit OS4, 14-16 days after insertion (approximately cycle day 20-22, or sooner if menses is expected to begin):

- The procedures described above for Visit OS2 will be completed, except that no OPK will be dispensed.
- A tentative appointment will be made for Visit OS5, taking into account the
  participant's usual cycle length and the need to have Visit OS5 take place before the
  participant's next menses begins but as late as possible in the cycle. The participant
  will be instructed to contact the site immediately if it appears that her menses is
  starting before Visit OS5.

# e) Visit OS5, 21-23 days after insertion (approximately cycle day 27-29, or sooner if menses is expected to begin):

- An acceptability questionnaire will be administered.
- Blood will be drawn for CBC, serum chemistries, and serum ferritin.
- The procedures described above for Visit OS2 will be completed, except that no OPK will be dispensed.
- Ovaprene™ will be removed and stored for later analysis.
- A colposcopic exam will be completed.
- Cervical mucus will be collected for ferrous gluconate and pH.
- The participant will next undergo an Ovaprene™ PCT cycle. She will be instructed to:
  - o Call at the onset of her next menses to tentatively schedule Visit OP1 on the day following the end of menses. Adjustments to this visit will be made as needed.
  - Use non-spermicidal, lubricated condoms (dispense as needed at this visit) from the first day of her next menses until day 10 of that cycle, and to abstain from intercourse and other vaginal activityr starting on Day 10 until after Visit OP2, the CMC visit.

<sup>q Assaying for ferrous gluconate in the cervical mucus is considered exploratory throughout the study.

"Other vaginal activity" includes insertion of vaginal medications/products other than the study product (prescription or over-the-counter), as well as insertion of sex toys, fingers, or anything else into the vagina. Tampons may be used during all days of menses in the Baseline PCT and Caya PCT cycles, but only during the first three days of menses in Ovaprene cycles.

Version: 06.00 (FINAL) Date: June 13, 2019

Blood for CBC, chemistries, ferritin																										✓
Note device position																										

Version: 06.00 (FINAL) Date: June 13, 2019

Vaginal samples for FG, pH, Nugent score, microflora, antibacterial activity, & soluble												_	-		
markers															
Device removed															
Colposcopy															
Cervical mucus for FG & pH															
Sex restrictions	No sex or other vaginal activity														

Version: 06.00 (FINAL) Date: June 13, 2019

